7.4.5.2.3 Rescue provisions for hypoglycemia

During insulin-induced hypoglycemia, plasma glucose levels as well as the patient status will be monitored closely throughout the procedure. After administration of trial product, if their glucose

levels become too low, patients may receive post-treatment IV glucose infusion to ameliorate hypoglycemia, as follows:

1. The IV glucose infusion should be initiated if a patient experiences escalating symptoms of hypoglycemia (e.g. start of moderate symptoms of hypoglycemia) at any time during the test procedure. Glucose infusion should then be initiated targeting a plasma glucose level >70 mg/dL
2. If plasma glucose is <54 mg/dL between t=8 and t=44 minutes, glucose infusion (e.g. 1-2 mg/kg administered over 5-10 seconds) should be initiated to maintain plasma glucose between 55 mg/dL and 70 mg/dL. Pause glucose infusion if plasma glucose is >70 mg/dL
3. If plasma glucose is <70 mg/dL at t \geq 45 minutes, glucose infusion (e.g. 2-3 mg/kg administered over 5-10 seconds) should be initiated to maintain plasma glucose between 70 mg/dL and 90 mg/dL. Pause glucose infusion if plasma glucose is >80 mg/dL

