7.4.5.2.1 Diabetes management

Last injection or bolus administration via continuous SC insulin infusion of any insulin medication should not take place within the 12 hours before dosing. Patients normally using insulin aspart will be switched to human soluble insulin or glulisine for the period between 12 and 10 hours prior to dosing, if needed. Patients using continuous SC insulin infusion will have their pump switched off at 22:00 hours.

To achieve a target glucose level of 90-160 mg/dL (5.0-8.9 mmol/L) in the morning of dosing, patients may be administered insulin glulisine and/or glucose at the discretion of the investigator by IV infusion using the following glucose infusion rate and insulin infusion rate as a guidance. Deviation from the guidance is allowed at the discretion of the investigator. Plasma glucose levels will be checked overnight at regular intervals in order to achieve and maintain the target plasma glucose level of 90-160 mg/dL (5.0-8.9 mmol/L).

A general guidance for administration of insulin IV and/or glucose IV at the dosing visit

Fluid infusion rate:

If plasma glucose < 300 mg/dL, then infusion of isotonic solution with 5% glucose:

Age 6–10 years: 80 mL/kg/24 h

Age >10 years: 60 mL/kg/24 h

If plasma glucose >300 mg/dL the glucose infusion will be substituted with fluid volume of normal saline (0.9% NaCl) at same infusion rate as above.

Insufion of insulin:

Insulin infusions should be performed with 0.5 IU insulin glulisine (Apidra®) per kg body weight in 48 mL NaCl 0.9% according to the following recommendations:

Glucose	Infusion rate	Insulin dose (IU/kg BW/h)
>200 mg/dL	10.0 mL/h	0.1
150–200 mg/dL	5.0 mL/h	0.05
80-150 mg/dL	2.5 mL/h	0.025
<80 mg/dL	Insulin infusion stop!	0

Abbreviation: BW=Body weight

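### Protocol 7.4.5.2.3: the example rescue glucose amounts do not fit the scale of the protocol's own infusion guidance, and rules 1 and 2 give a symptomatic child below 54 mg/dL two targets that do not overlap

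*Protocol*

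**What the plan says.** Protocol 7.4.5.2.3 has three rules for IV glucose after trial product. The wording is the same in both copies of the protocol.

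- **Rule 1** is triggered by symptoms: "The IV glucose infusion should be initiated if a patient experiences escalating symptoms of hypoglycemia", and it applies "at any time during the test procedure". Its aim: "Glucose infusion should then be initiated targeting a plasma glucose level >70 mg/dL".
- **Rule 2** is triggered by a value: "If plasma glucose is <54 mg/dL between t=8 and t=44 minutes". Then "glucose infusion (e.g. 1-2 mg/kg administered over 5-10 seconds) should be initiated to maintain plasma glucose between 55 mg/dL and 70 mg/dL", and "Pause glucose infusion if plasma glucose is >70 mg/dL".
- **Rule 3** covers values below 70 mg/dL from 45 minutes on. Its example is 2-3 mg/kg over the same few seconds, its band is 70-90 mg/dL, and it adds: "Pause glucose infusion if plasma glucose is >80 mg/dL".

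The section does not derive the mg/kg amounts, give a repeat interval, or say which rule prevails when a child meets two.

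The other place with glucose quantities is 7.4.5.2.1. Its guidance for the dosing visit reads, for glucose below 300 mg/dL, "then infusion of isotonic solution with 5% glucose", at 80 mL/kg/24 h for ages 6-10 and 60 mL/kg/24 h above 10. The overnight and morning target is 90-160 mg/dL. Investigators may depart from this guidance.

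**The concern.** Rescue is the main protection for children who are deliberately made hypoglycemic, including those on placebo. Section 5.3 calls the risk of the induction procedure minimal and well controlled, and relies in part on the predefined thresholds for IV glucose.

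Two things in the rules look wrong. The example amounts are very small next to the glucose the same protocol runs overnight, which raises the question whether a quantity, a unit or a time base is misstated. And a child can meet two rules that ask for different glucose levels. Either could lead sites to treat the same child differently.

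**Working it through.** **Inputs.** Rescue amounts, delivery time, bands and pause values: Protocol 7.4.5.2.3. Infusion rates and concentration: 7.4.5.2.1, with 5% read as 50 mg/mL. Blood volume: section 5.3 (Germany-only text), which equates 1% of blood volume with about 18 mL at 20 kg. Frequency of glucose checks: 7.4.5.2.2.

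**Is the guidance block itself sound?** The protocol gives no derivation of the rescue amounts to reproduce. The insulin table beside the glucose rates can be checked. With 0.5 IU/kg in 48 mL, 10, 5 and 2.5 mL/h give 0.5/48 × rate = 0.104, 0.052 and 0.026 IU/kg/h. The printed values are 0.1, 0.05 and 0.025, so the block agrees with itself after rounding.

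**Overnight glucose rate** = mL/kg/24 h × 50 / 1440.

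- Age 6-10: 80 × 50 / 1440 = 2.78 mg/kg/min.
- Age above 10: 60 × 50 / 1440 = 2.08 mg/kg/min.

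**Rescue amount as time on that infusion** = amount / rate.

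| Amount | Age 6-10 | Age above 10 |
|---|---|---|
| 1 mg/kg | 22 s | 29 s |
| 2 mg/kg | 43 s | 58 s |
| 3 mg/kg | 65 s | 86 s |

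Rule 2's amount is thus 22-58 s of the overnight infusion, and rule 3's is 43-86 s. For a 20 kg child, 1-2 mg/kg is 20-40 mg, or 0.4-0.8 mL of the 5% solution.

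**Reading A: the amount is given once.** Section 5.3 implies 18 / 0.01 / 20 = 90 mL/kg, or 0.9 dL/kg. If all the glucose stayed in that volume, the rise is 1/0.9 to 2/0.9 = 1.1-2.2 mg/dL. With a distribution space of 1.5-2.5 dL/kg (an assumption; the documents give none), it is 1/2.5 to 2/1.5 = 0.4-1.3 mg/dL. A child at 50 mg/dL needs 5 mg/dL to reach rule 2's floor of 55. For 2 mg/kg to supply that, the space would have to be 2/5 = 0.4 dL/kg, less than half the implied blood volume.

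**Reading B: one amount per glucose check.** Checks are about every 5 minutes until glucose is back to 70 mg/dL. That is 1/5 to 2/5 = 0.2-0.4 mg/kg/min, which is 5 (2.08/0.4) to 14 (2.78/0.2) times below the overnight rate.

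**Reading C: delivery continues at the stated pace.** 1 mg/kg per 10 s is 6 mg/kg/min and 2 mg/kg per 5 s is 24 mg/kg/min, about 2 (6/2.78) to 12 (24/2.08) times the overnight rate.

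For the same mg/kg amount, readings B and C differ by a factor of 300/10 = 30 to 300/5 = 60.

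**Rules 1 and 2 side by side.** Take a child with escalating symptoms and glucose below 54 mg/dL at 8-44 minutes. Rule 1 applies because it has no time limit, and it aims above 70. Rule 2 applies on value and time; it holds 55-70 and pauses above 70. No glucose level satisfies both.

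**Reach into the analysis.** Protocol 10.1.3.2 and SAP 11.1 set any rescued patient to not recovered, censored at 45 minutes, whatever the amount. Change from baseline uses the value at the time of rescue (SAP 11.2). Time to first infusion (SAP 14.1.4) depends on the trigger, not the amount. The exception is the first sensitivity analysis in SAP 11.1, which does not censor for rescue. Dosing requires glucose from 54 to below 80 mg/dL, so recovery (+20) needs 74 to just under 100. Rule 2's pause above 70 works against reaching that; rule 1's open-ended target allows it.

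**The case against.** The strongest reply is that nothing in rule 2 makes 1-2 mg/kg the whole treatment. The rule speaks of maintaining a range and of pausing, so delivery is repeated or continued until the range is met. This stands. A reader might infer from reading A that the rescue dose is shown to be too small; the documents do not support that, because a single dose is only one way to read them. The reply does not settle how the glucose is to be given, since the remaining readings lie 30- to 60-fold apart.

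A reader might also infer that the rescue figures contradict the infusion guidance. That is too strong. The overnight infusion runs alongside insulin toward 90-160 mg/dL and is stopped at least 30 minutes before planned dosing, and IV insulin stops below 80 mg/dL. Both texts are guidance: one is an example, the other allows deviation. What stands is a mismatch of scale.

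Rule 3's pause above 80 inside a 70-90 band might be taken for an error. It can equally be overshoot control, and nothing requires the pause to equal the upper limit.

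Finally, the clash between rules 1 and 2 needs both triggers; a child without symptoms falls under rule 2 alone. Frequent checks, extra measurements at discretion and, in Germany, mandatory termination if safety may be at risk also protect the child. These limit the harm but do not tell a site which target to follow.

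**Conclusion.** The concern holds in two parts.

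First, the amount, unit and mode of delivery in rules 2 and 3 are unresolved. The examples equal 22-58 s (rule 2) and 43-86 s (rule 3) of the protocol's own overnight infusion. Rule 2's amount is either far too little to lift a child from 50 to 55 mg/dL in one delivery or, if continued at its stated pace, 6-24 mg/kg/min. The time equivalents rest only on protocol figures. The 1.1-2.2 mg/dL rise rests on single delivery into the implied blood volume, and the 0.4-1.3 mg/dL rise on an assumed space. The 50 mg/dL child is an example: one just under 54 could cross the trigger after one delivery.

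Second, rules 1 and 2 set non-overlapping targets, without precedence, for a symptomatic child below 54 mg/dL at 8-44 minutes.

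A reader might infer that the trial's efficacy results are distorted. They are not through the primary analysis, change from baseline or time to first infusion. Only the analysis without censoring for rescue could move, and the documents do not allow that effect to be sized. The weight of the point is that this is safety text for children and cannot be followed in one way.

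**What to change.** The sponsor and investigators should:

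- check the amount, unit and mode of delivery in rules 2 and 3 against 7.4.5.2.1, and reconcile the two sections;
- reconcile rules 1 and 2 for a child who meets both;
- confirm whether rule 3's pause value is intended, given its stated band.

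No amount, target or order of precedence is proposed here; those are clinical decisions. The cost is protocol wording and a note to sites, with no added procedures or patients.

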7.4.6 Selection of doses in the trial

The selected dose of 1 mg GlucaGen[®] is the recommended dose for treatment of severe hypoglycemia (in accordance with the label, children below 25 kg body weight will be administered 0.5 mg GlucaGen[®]). Pre-clinical and adult clinical studies demonstrated that 0.6 mg of dasiglucagon results in an initial PD response (i.e. acute glucose mobilization) comparable to 1 mg GlucaGen[®].

The estimation of the dasiglucagon dose in the pediatric trial is based on a PK and PD approach⁶ where a previously developed population PK/PD model³ for dasiglucagon was extended with an allometric scaling component for the PK model⁴. The PD response was assumed to be similar in pediatric and adult patients as organ maturation for patients above 4 years is assumed not to have a meaningful impact on dasiglucagon PD. The pediatric PK component was developed by allometric scaling of clearance (Cl) and volume (V) by body weight from published glucagon PK data obtained from 2 clinical trials following intramuscular administration to pediatric (4 to 17 years) and adult T1DM patients^{11,9}.

The conclusion of the modelling was that a dose of 0.6 mg appears appropriate to ensure a fast rescue from hypoglycemia for adult patients and children down to a weight of 25 kg. Although the dasiglucagon C_{max} and AUC is expected to be higher in children, it does not exceed the total C_{max} and AUC obtained in adults previously administered 2 mg dasiglucagon. The higher total drug exposure (AUC and C_{max}) at lower weight is partially compensated by the shorter t_{1/2} and saturated PD response. The resulting total time of drug exposure and PD effect (AEU and CE_{max}) is similar throughout the weight range.

7.4.7 Collection of blood samples

The total blood volume to be obtained from any individual child will be about 43 mL. The maximum amount per visit is 12 to 17 mL. These values are within the recommended scope provided by the EU⁵.

The following blood volume will be taken for each sample at each visit:

Sample type	Visit 1 (mL)	Visit 2 (mL)	Visit 3 (mL)
Biochemistry/pregnancy	5.00	-	5.00
Hematology	2.00	-	2.00
Coagulation	2.00	-	2.00
HbA1c	2.00	-	-
ADA	3.00	-	3.00
PK	-	4.00	-
PD	-	12.00	-
Onsite-PG	-	1.00	-
Sum for each visit	14.00	17.00	12.00
Total			43.00

Abbreviations: ADA=Anti-drug antibodies; HbA1c=Hemoglobin A1c; Onsite-PG=Onsite monitoring of plasma glucose; PD=Pharmacodynamics; PK=Pharmacokinetics

7.4.8 Treatment compliance

Unblinded trial personnel will handle, prepare and administer all trial products.

7.4.9 Method of assigning patients to treatments

Forty patients will be randomized in a 2:1:1 ratio (dasiglucagon/placebo/GlucaGen®) into the 3 treatment arms and stratified in 2 age groups: 6 to ≤12 years and 12 to ≤18 years and by injection site (abdomen/thigh). A minimum of 16 patients will be enrolled into each age group, including a minimum of 8 patients in either of age groups on dasiglucagon treatment arm.

Patients who meet the inclusion and exclusion criteria will be randomized into one of the following treatment arms:

- Dasiglucagon, liquid formulation, 1 mg/mL, 0.6 mL
- Placebo treatment: Placebo, liquid formulation, 0.6 mL
- Active control treatment: Recombinant glucagon hydrochloride, 1 mg lyophilized powder for reconstitution (GlucaGen®, Novo Nordisk) in 1 mL sterile water (in accordance with the label, children below 25 kg body weight will be administered 0.5 mg GlucaGen®)

Randomization will be performed using a central, dynamic variance minimization randomization method using an interactive web response system (IWRS) that will randomize a patient to one of the 3 aforementioned treatment arms and then assign dispensing unit numbers to that patient.

An unblinded statistician/programmer who is separate from the trial team will generate the randomized kit list before the initiation of the trial.

Treatment assignment will be kept strictly confidential and accessible only to authorized persons until after data base lock. However, the investigators can perform an emergency unblinding within the IWRS in case of an emergency, see [Section 7.4.10](#).

7.4.10 Blinding and breaking the blind

This is a double-blind trial. Dasiglucagon is available as a liquid formulation and GlucaGen® is available as a powder for reconstitution; they are therefore not identical in appearance. Unblinded trial personnel will be responsible for handling, preparing (according to the prescription from the IWRS), and administering the trial product, and the syringes used for administration will be wrapped in aluminum foil to maintain the blinding at bedside. Parents being in the room with their child must be instructed not to look while the unblinded staff is administering the injection. To maintain double-blind conditions, blinded trial personnel not involved in the administration of trial

products will perform all trial assessments at the trial center and is responsible for keeping the records strictly confidential and accessible only to the unblinded staff. However, unblinded personnel at the specialty laboratories will perform the exposure assessments and ADA assessments to make sure that dasiglucagon or GlucaGen® administration is matched with the applicable bioanalytical assay.

Treatment assignment will be kept strictly confidential and accessible only to authorized persons until after the time of unblinding (database lock). Codes with treatment assignment will however be readily available in the IWRS to the blinded personnel in case of an emergency.

The code for a particular patient may be broken in a medical emergency if knowing the identity of the treatment allocation would influence the treatment of the patient. The emergency code break can be performed using the IWRS. Whenever a code is broken, the person breaking the code must record the time, date and reason as well as his/her initials in the source documents.

The breaking of blinded codes in case of medical emergency for a patient should not unblind the trial personnel to the treatment information of other patients. The person performing the unblinding should inform as few people as possible about the result of the unblinding. All persons unblinded for a specific patient should be documented.

If the trial center needs to break the code, the medical monitor should, if at all possible, be contacted prior to breaking the code and the monitor must be notified within 24 hours after the code has been broken.

7.4.11 Drug accountability and disposal

Unblinded trial personnel will do the handling, preparation and administration of trial product. Each center will keep accurate records of the trial supplies received, stored, and dispensed, using appropriate forms. The trial supplies will be stored under appropriate conditions, locked and with restricted access. The unblinded monitor will perform the drug accountability to ensure compliance.

All unused supplies and all empty and partially empty containers of trial product will be stored until the trial closure visit has been performed and then sent to the sponsor.

7.4.12 Prior and concomitant therapy

All concomitant medications will be recorded in the eCRF at each visit.

Prior to the start of the clamp procedure, the patient's eligibility must be checked. If the patient has taken any prohibited medication, he/she will be excluded from the dosing visit but may be rescheduled 1-7 days later. Each patient may only have their dosing visit rescheduled once. See [Section 7.3.3.1](#) for possible reasons for patient discontinuation.

7.4.13 Treatment after end of trial

After the end of their trial participation, patients should return to the standard of care that they received prior to enrollment in the trial. The treating physician will be responsible for supervising patients after the end of the trial.

7.5 Assessments and schedule of measurements

The following assessments and measurements will be carried out at the times specified in the trial schedule of assessments ([Table 2-1](#)).

Informed consent will be obtained prior to any trial-related procedures; see [Section 11.3](#).

7.5.1 Screening visit

At screening (Visit 1), the following assessments will take place:

- Informed consent
- Inclusion/exclusion criteria
- Demography
- Body measurements
- Diabetes diagnosis, and current diabetes treatment
- Medical history including concomitant illnesses
- Prior and concomitant medications
- History of alcohol/drug abuse
- Physical examination
- Vital signs
- 12-lead ECG
- AEs
- Biochemistry, hematology, coagulation, hemoglobin A1c (at Visit 1 only)
- Serum pregnancy test (female patients of childbearing potential only)
- Urinalysis
- Antibodies against dasiglucagon/GlucaGen®

7.5.2 Dosing visit

At Visit 2 (Day 0), patient eligibility is rechecked (check of changes between the screening visit and Visit 2) and patient's eligible to participate will be randomized to treatment with dasiglucagon, placebo or GlucaGen®.

The following assessments will take place:

- Inclusion/exclusion criteria (prior to the start of the insulin-induced hypoglycemic procedure. Only check of exclusion criteria at clinic admission on Visit 2, day 0 and changes between screening visit and Visit 2)
- Concomitant medications (prior to the start of the insulin-induced hypoglycemic procedure)
- Current diabetes treatment
- Randomization (prior to the start of the insulin-induced hypoglycemic procedure)
- Exclusion criteria at clinic admission on Visit 2, day 0 (prior to the start of the insulin-induced hypoglycemic procedure)
- Urine stick pregnancy test (women of childbearing potential only) (prior to the start of the insulin-induced hypoglycemic procedure)
- Urinalysis (prior to the start of the insulin-induced hypoglycemic procedure)
- Alcohol breath test (prior to the start of the insulin-induced hypoglycemic procedure)
- Physical examination (prior to the start of the insulin-induced hypoglycemic procedure)
- Insulin-induced hypoglycemia

- Vital signs (prior to the start of the insulin-induced hypoglycemic procedure (within 30 minutes), and at 30, 60 and 300 minutes after dosing. The actual time of the assessment should not deviate from the nominal time by more than ± 10 minutes)
- 12-lead ECG (prior to the start of the insulin-induced hypoglycemic procedure (within 30 minutes), and at 20, 35, 45, 60 and 300 minutes after dosing. The actual time of the assessment should not deviate from the nominal time by more than ± 5 minutes)
- Local tolerability (at 30, 120, and 300 minutes after dosing. The actual time of the assessment should not deviate from the nominal time by more than ± 10 minutes)
- AEs
- Plasma dasiglucagon/GlucaGen® (pre-dose, and at 10, 20, 30, 40, 60, 90, 140, 220, and 300 minutes after dosing. The actual time of blood sampling should not deviate from the nominal time by more than ± 1 minute between $t=5$ minutes and $t=90$ minutes, ± 5 minutes between $t=150$ minutes and $t=240$ minutes. Pre-dose is defined as within 2 minutes prior to dosing)
- Plasma glucose (pre-dose, and at 4, 6, 8, 10, 12, 15, 17, 20, 30 and 45 minutes (and as well at 60 minutes if the patient's body weight is ≥ 21 kg) after dosing. The actual time of blood sampling should not deviate from the nominal time by more than ± 30 seconds until the 20-minute collection time point, and by more than ± 1 minute for the subsequent collection time points. Pre-dose is defined as within 2 minutes prior to dosing)
- Administration of trial product (during hypoglycemic clamp procedure)

7.5.3 Follow-up visit

At 28 (+ 5) days after the hypoglycemic clamp procedure, the follow-up visit is scheduled to collect safety data. The following assessments will take place:

- Concomitant medications
- Current diabetes treatment
- Physical examination
- Vital signs
- 12-lead ECG
- Local tolerability
- AEs
- Biochemistry, hematology, coagulation, HbA1c (HbA1c at Visit 1 only)
- Urine stick pregnancy test (women of childbearing potential only)
- Urinalysis
- Antibodies against dasiglucagon/GlucaGen® (any treatment-induced or treatment-boosted [titer increase above 5 fold] ADA-positive patients will be monitored until the ADA levels return to baseline levels)

7.5.4 Final examination at the end of the trial

The final visit of the trial is Visit 3 (Day 28[+5] of the follow-up period; end-of-trial visit). See Section [7.5.3](#) for further details.

7.5.5 Additional (safety) examinations

If there are any unclear symptoms or observations the responsible physician in charge may perform further medical examinations, other than outlined in this protocol, including further clinical laboratory tests, in order to clarify the relevance or to diagnose symptoms.

